11.2.2 General summaries of TEAEs

Pre-treatment AEs will be provided in a subject data listing; no summaries of pre-treatment AEs are planned.

An overall summary of AEs will provide the overall number of TEAEs and the numbers and percentages of subjects with at least 1 TEAE, with a TEAE that led to permanent discontinuation of study drug, with a drug-related TEAE, with a severe TEAE, with a treatment-emergent SAE, and with a drug-related treatment-emergent SAE. The number and percentage of subjects who died will also be summarized. This summary will be provided for all subjects in the Safety Analysis Set and also by subgroup for geographic region and indication.

The following summaries of TEAEs will be provided by MedDRA SOC and PT. All summaries are for the combined Evaluation, Down-Titration, and Post-Treatment Periods unless otherwise indicated.

Overall Incidence Summaries

- Incidence of TEAEs
- Incidence of TEAEs by 3-month time interval
- Incidence of TEAEs by study period (Evaluation, Down-Titration, Post-Treatment)
- Incidence of TEAEs for TEAEs occurring in at least 5% of subjects

- Incidence of TEAEs by 3-month time intervals for TEAEs occurring in at least 5% of subjects overall
- Incidence of non-serious TEAEs occurring in at least 5% of subjects

The incidence of TEAEs occurring in at least 5% of subjects will be summarized overall as noted above and also by subgroup for geographic region, indication, and randomized treatment from the previous double-blind study.

A subject is included in a 3-month interval if the subject was receiving BRV at any time during that interval based on their duration of exposure to BRV (eg, a subject with exposure for 91 days is included in the time interval for Months 1-3 and Months 4-6). Summaries of AEs by 3-month intervals will include all subjects who are classified into each time interval as defined above. TEAEs which had onset prior to or on the date of the last dose of BRV are included in summaries by 3-month time intervals.

Maximum Intensity and Causality

- Incidence of TEAEs by maximum intensity
- Incidence of drug-related TEAEs

Serious Adverse Events

- Incidence of treatment-emergent SAEs

Discontinuations due to TEAE

- Incidence of TEAEs leading to permanent discontinuation of study drug

TEAEs of interest

AEs of interest will be identified based on MedDRA search criteria, which are documented outside of the SAP. The following summaries will be provided for AEs of interest:

- Incidence of TEAEs of interest
- Incidence of TEAEs of interest by 3-month time interval

For the summary by maximum intensity, each subject will be counted at most once per SOC or PT according to the maximum intensity of all AEs within that SOC or PT. Severe intensity will be assumed for AEs for which intensity is not specified.

Drug-related AEs are AEs for which the relationship to study drug is specified as Related or AEs for which relationship is not specified.

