5. BACKGROUND INFORMATION

5.1 Background and epidemiology of targeted disease

Epilepsy is one of the most common and challenging neurological disorders. It has been estimated that over 50 million people are affected worldwide^(1, 2, 3, 4). The prevalence of epilepsy is around 1%. The annual incidence in developed countries is approximately 50 to 70 cases per 100,000. In developing countries, the figure is higher due to more limited obstetric services and the greater likelihood of cerebral infection and trauma. The incidence varies greatly with age, with high rates occurring in childhood, falling to low levels in early adult life, but with a second peak in those aged over 65 years. In many people, particularly children, the condition may remit, although a significant proportion will have epilepsy lifelong. The disease duration is often determined by the underlying cause. Sudden unexpected death, a complication of great concern, occurs in 1 to 5 per 1000 patient years, particularly if the seizure disorder remains uncontrolled. The treatment for epilepsy remains difficult, and there is an ongoing medical need for new antiepileptic drugs (AEDs). For a considerable proportion of patients, seizure freedom can still not be reached with currently available AEDs^(5, 6).

Diagnosis of epilepsy is based on the recurrence of seizures. Seizures may be caused by an underlying brain disorder or lesion or due to genetic conditions. Characterization of the epileptic syndrome has profound implications for treatment and prognosis. The major dichotomy for the diagnosis of epilepsy is the differentiation between focal epilepsies (ie, related to a focal brain dysfunction), which are the most frequent and account for approximately 60 to 70% of all cases, and generalized epilepsy syndromes, which represent approximately 25 to 30% of all epilepsy syndromes. In about 10% of cases, other specific syndromes are classified or the classification remains uncertain.

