7. STUDY DESIGN

7.1 Type/Design

This is a therapeutic long-term follow-up, multinational, multi-center, noncomparative, open-label and single arm study.

This long-term follow-up study will run throughout the duration of the clinical development period of brivaracetam, and will thus include therapeutic exploratory studies in the early stage of development as well as therapeutic confirmatory studies, in the later stage of the development. For this reason, the study design and in particular the frequency of study visits is adapted to the 3 types of study, as described below:

For subjects coming from the therapeutic exploratory study (N01114):

- First year:
 - First 6 months: 1 visit/month: 1 FEV alternately with 1 MEV.
 - Next 6 months: 1 visit/3months: 2 FEV (at V7 and V8).
- Second and subsequent years:
 - 1 visit/3months: 1 FEV alternately with 1 MEV.
 - Yearly Evaluation Visit will be performed in replacement of the first FEV of each year.

For subjects coming from confirmatory studies (N01252 and N01254):

- First year:
 - First 3 months: 1 visit/month: FEV alternating with MEV.
 - Next 9 months: 1 visit/3 months: FEV alternating with MEV.
- Second and subsequent years:
 - 1 visit/3months: FEV alternating with MEV.
 - Yearly Evaluation Visit will be performed in replacement of the first FEV of each year.

For subjects coming from ULD confirmatory studies (N01187 and N01236):

- First year:
 - First 3 months: 1 visit/month: 1 FEV alternating with 1 MEV.
 - Next 9 months: 1 visit/3months: FEV alternately with MEV.
- Second and subsequent years:
 - 1 visit/3months: 1 FEV alternating with 1 MEV.
 - YEV will be performed in replacement of the first FEV of each year.

For subjects coming from long-term follow up study (N01315):

- Subjects will perform their Last Visit in N01315 and perform at the same time their First Visit in N01125. They will follow the schedule of 1 visit/3 months: 1 Full Evaluation Visit alternating with 1 Minimal Evaluation Visit. Yearly Evaluation Visit will be performed in replacement of the first Full Evaluation Visit of each year.

This document cannot be used for regulatory submission and any alterations or variations thereof.

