11.1 Extent of exposure

A daily dose will be calculated for each study day from the day of first dose of BRV to the day of last dose of BRV for the purposes of calculating modal dose. Daily dose will be calculated as the sum of the AM and PM dose for each day.

Modal daily doses will be calculated across all study days on or after the day of first dose of BRV and up to and including the day of last dose of BRV. Modal daily dose is the most frequently taken daily dose during this period. In the event of a tie, the modal dose will be set to the lower of the tied doses. Modal daily dose will be categorized as follows:

Category	Definition
5 mg/day	<20mg/day
20mg/day	≥20mg/day to <50mg/day
50mg/day	≥50mg/day to <100mg/day
100mg/day	≥100mg/day to <150mg/day
150mg/day	≥150mg/day to <200mg/day
200mg/day	≥200mg/day

Subject years of exposure will be calculated by summing the exposure duration in days for all subjects being summarized, and dividing the resulting value by 365.25.

Subject years of exposure will be presented overall and by modal dose for the Safety Analysis Set. The subject years of exposure presented by modal dose will be the total subject years of exposure of subjects with that modal dose.

The number and percentage of subjects exposed to BRV will be summarized overall and by modal dose category. The number and percentage of subjects in each Exposure Duration Cohort (≥ 3 months, ≥ 6 months, ≥ 12 months, and so forth) will be summarized.

The number and percentage of subjects within each modal dose category will be summarized for each Exposure Duration Cohort; percentages will be relative to the total number of subjects in each Exposure Duration Cohort.

In addition to the overall summaries of the above, the above will also be summarized by subgroup for region (North America, Europe [EU member states], Europe [non-EU member states], Asia/Pacific/Other), and by indication (Partial Onset Seizures, Primary Generalized Seizures, ULD).

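### SAEs, TEAEs leading to discontinuation and deaths are planned only as crude percentages despite very unequal follow-up, and the SAP leaves out the exposure-category tables that the protocol specifies

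*SAP*

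**What the plan says.** The overview table in SAP 11.2.2 reports "the numbers and percentages of subjects with at least 1 TEAE, with a TEAE that led to permanent discontinuation of study drug", and treats drug-related TEAEs, severe TEAEs and SAEs in the same way. For deaths: "The number and percentage of subjects who died will also be summarized". On subgroups: "This summary will be provided for all subjects in the Safety Analysis Set and also by subgroup for geographic region and indication". The table of TEAEs occurring in at least 5% of subjects is further split "by subgroup for geographic region, indication, and randomized treatment from the previous double-blind study". Unless stated otherwise, the tables by preferred term pool the Evaluation, Down-Titration and Post-Treatment Periods. One table shows TEAEs by study period.

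There is some time-sliced output. The list includes "Incidence of TEAEs by 3-month time interval", with matching tables for TEAEs in at least 5% of subjects and for TEAEs of interest. A subject counts in an interval if on brivaracetam at any time during it.

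Person-time appears only in the exposure section, SAP 11.1: "Subject years of exposure will be presented overall and by modal dose for the Safety Analysis Set". The same section repeats the exposure summaries by indication and for four named regions.

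On the protocol side, section 13.3.1 notes that subjects leave at different times and says results will therefore be shown by exposure-duration category. Section 13.1.3 applies this to TEAEs and calls for separate tables of that kind for SAEs and for AEs leading to withdrawal. Section 7.1 says the study "will thus include therapeutic exploratory studies in the early stage of development as well as therapeutic confirmatory studies". Section 5.1 gives an epidemiological figure: "Sudden unexpected death, a complication of great concern, occurs in 1 to 5 per 1000 patient years".

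**The concern.** A percentage of subjects with an event depends on how long they were watched. Follow-up here is unequal by design. Source studies fed in from early to late development, while closure depends on programme-wide events (Protocol 7.4). Exposure cohorts start at one day (SAP 3.2.7), and Kaplan-Meier retention is planned out to 60 months (SAP 5.1).

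Indication is tied to source study: the generalized-seizure subjects come only from N01254 and the ULD subjects only from N01187 and N01236 (Protocol 13.1.1). Mean exposure can therefore differ by indication, and by region where source studies drew on different countries. A higher SAE percentage in one indication could reflect longer observation alone. The study-period table has the same weakness, because it sets an Evaluation Period that can last years beside a drug-free period of two to four weeks (SAP 2.3).

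At stake is the reading of two of the three primary safety variables (SAEs and withdrawal due to AE) and of mortality. These have neither an interval table nor a person-time denominator.

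**Working it through.** **Inputs from the documents.** Enrolled: 859, of whom 6 came from N01315 (SAP 2.4). The Safety Analysis Set excludes those 6 and requires a dose (SAP 3.5.1), so its maximum size is 859 − 6 = 853. Exposure is last dose minus first dose plus one day (SAP 3.2.7); subject-years are summed days / 365.25 (SAP 11.1).

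**Inputs that are assumptions.** The documents give no hazards, event counts, mean exposure or total subject-years, so there is no planned figure to reproduce. All values below for these are illustrative.

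**1. Which results have any handling of follow-up time?**

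| Result | 3-month intervals (SAP) | Exposure category (protocol) | Exposure category (SAP) | Subgroups (SAP) | Per subject-year (SAP) |
|---|---|---|---|---|---|
| Any TEAE | yes | yes | no | region, indication | no |
| TEAEs in ≥5% | yes | within TEAEs | no | region, indication, prior treatment | no |
| TEAEs of interest | yes | not named | no | none | no |
| SAEs | no | yes | no | region, indication | no |
| Discontinuation or withdrawal due to AE | no | yes | no | region, indication | no |
| Deaths | no | not named | no | region, indication | no |

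The SAP uses its exposure-duration cohorts for seizure outcomes (8.1.1 to 8.1.3) and for modal dose (11.1), but for no AE table. None of the interval tables is planned by subgroup, and a subject exposed for part of an interval counts in full.

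**2. Same risk, different follow-up.** With constant hazard h per year and follow-up T years, the crude proportion is p = 1 − exp(−hT).

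- h = 0.05: T = 1, 3, 5 gives 4.9%, 13.9%, 22.1%.
- h = 0.10: T = 1, 3, 5 gives 9.5%, 25.9%, 39.3%.
- h = 0.10, T = 6: 1 − exp(−0.6) = 45.1%. Against 25.9% at 3 years the gap is 45.1 − 25.9 = 19.2 points with no difference in risk.
- Study periods, h = 0.10: a four-week drug-free period gives 1 − exp(−0.1 × 28/365.25) = 0.76%, against 25.9% for a three-year Evaluation Period.

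**3. Deaths.** Assume 12 deaths. The crude figure is 12/853 = 1.4% whatever the exposure. The rate is 1000 × 12/Y for Y subject-years. Exact Poisson limits for a count of 12 are χ²(0.025; 24)/2 = 6.20 and χ²(0.975; 26)/2 = 20.96.

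| Assumed subject-years | Mean per subject (Y/853) | Deaths per 1000 subject-years (95% CI) |
|---|---|---|
| 2000 | 2.3 years | 6.0 (3.1 to 10.5) |
| 4000 | 4.7 years | 3.0 (1.6 to 5.2) |
| 6000 | 7.0 years | 2.0 (1.0 to 3.5) |

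These are deaths from any cause and only show how much the denominator matters. They are not comparable with the protocol's figure, which is for sudden unexpected death.

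**4. Can the planned output be turned into rates?** Overall, by indication and for four regions, yes, roughly: deaths or SAEs can be divided by the subject-years in SAP 11.1. By prior randomized treatment, no, because subject-years are not planned for that split. Latin America is a region in SAP 4.8 but is not among those named in SAP 11.1. The division is also only approximate: exposure stops at the last dose, while AE tables include a Post-Treatment Period that SAP 3.2.4 leaves without an end date.

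**The case against.** The strongest reply is that this is a single-arm, noncomparative study with no hypothesis test (SAP 3.1), that the 3-month tables already deal with unequal follow-up for TEAEs and show timing that a single rate hides, and that a reader has the subject-years needed to form a rate. Much of this stands, and it rules out several stronger readings.

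- A reader might infer that every AE result is a crude percentage. The three interval tables show otherwise. They do not separate out SAEs, discontinuations or deaths, and they are not produced by subgroup.
- A reader might infer that deaths cannot be related to person-time. They can be, approximately, overall, by indication and for the listed regions. The plan simply does not do it.
- A reader might infer that the split by prior treatment is confounded by follow-up. The documents do not show this. Treatment was randomized within each source study, so staggered entry alone does not separate placebo from brivaracetam; differing allocation mixes or dropout would be needed. Only the table of TEAEs in at least 5% of subjects uses this split.
- A reader might take the sudden-death figure in Protocol 5.1 as the plan's mortality benchmark. It is disease background, covers one cause of death, and is tied to no analysis.

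It is also fair to say that no actual imbalance in exposure is documented. The reply does not explain why the exposure-category tables in Protocol 13.1.3 and 13.3.1 have no counterpart in the SAP.

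**Conclusion.** The concern holds for SAEs, TEAEs leading to discontinuation and deaths, and for the subgroup and study-period percentages generally. These mix risk with length of observation, and the safeguard that the protocol specified is missing from the SAP without a stated reason. The possible size is material: a gap of about 19 points at equal risk in one illustration, and a threefold range of death rates behind the same 1.4% in another. Both rest on assumed hazards, deaths and exposure, and the second also on 853, which is the maximum size of the Safety Analysis Set. The change should be made. It bears on how the primary safety objective is interpreted; no test or error rate depends on it.

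**What to change.** 1. In SAP 11.2.2, for any TEAE, SAE, TEAE leading to discontinuation and TEAEs of interest, add subjects with an event per 100 subject-years, and for deaths per 1000, with exact Poisson 95% confidence intervals. Give these overall and in the subgroups already planned for each table, and keep the percentages alongside.
2. Match numerator and denominator. Count events with onset from first to last dose over time to first event or last dose. Count deaths over time to death or last contact. Show post-treatment events separately over time to last contact, since that period has no defined end.
3. Restore the tables of TEAEs, SAEs and AE withdrawals by category of total exposure, using the cohorts already defined in SAP 3.2.7.
4. Add subject-years to SAP 11.1 for any subgroup used in an AE table but missing there, namely prior randomized treatment and Latin America.
5. Compare with the background of 1 to 5 per 1000 patient-years only for deaths classified as sudden unexpected death.

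The cost is modest: extra columns, a few tables and a small new derivation of time to first event. Item 5 also needs deaths classified by cause. A single rate assumes a roughly constant hazard over years of treatment, which is why the percentages and the 3-month tables should stay.

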13.1.3 Statistical Evaluation

- General considerations:

Summary statistics will consist of frequency tables for categorical variables and descriptive statistics (number of available observations, mean, median, standard deviation, minimum, maximum, 25th and 75th percentiles) for continuous variables.

The periods considered are:

- Evaluation Period (V1 until the last Evaluation Visit).
- Down-Titration Period.
- Post-treatment Period.

Efficacy summaries will be created separately for the POS and PGS subpopulations within the efficacy population, and safety summaries will be created for the safety population and separately for the POS, PGS, and ULD subpopulations within the safety population.

- Baseline:

Baseline, whether efficacy or safety, will always refer to the original prior study pretreatment Baseline value. Baselines created and validated, as part of the prior study SAPs, will be copied and used by this study for all change from Baseline analyses.

- Study entry/disposition:

Subjects will be sufficiently described to enable a clear understanding of the populations and subpopulations and relevant demographics, disease, medical history, current treatment(s), as well as disposition. Historical and Baseline data will be copied from the prior study as required by the SAP.

- Seizure efficacy variables:

Analyses will be based upon the Efficacy Population. Summaries will be over the entire Evaluation Period and by 3-month periods over the Evaluation Period. The ULD subpopulation seizure diary data will not be summarized.

This document cannot be used to support any marketing authorization application and any extensions or variations thereof.

- QOLIE-31-P and EQ-5D efficacy variables:

Analyses will be based upon the Efficacy Population and summarized by data collection scheduled visits and for the last Evaluation Period assessment during the first 2 years. Data collected after year 2 are not planned to be summarized. The ULD subpopulation QOLIE-31-P and EQ-5D data will not be summarized.

- Pharmacoeconomic variables:

Analyses will be based upon the Efficacy Population and summarized by 3-month periods. Data collected after year 2 are not planned to be summarized. The ULD subpopulation pharmacoeconomic data will not be summarized.

- Safety variables:

Analyses will be based upon the Safety Population. Summary tables will be presented over the Evaluation Period by time windows, by periods, and by categories of total duration of exposure.

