Treatment-emergent adverse events will be summarized by categories of total duration of exposure, period, and Medical Dictionary for Regulatory Activities (MedDRA[®]) Primary System Organ Class and Preferred Term in incidence tables. Separate tables will be provided, by categories of total duration of exposure, for AEs leading to withdrawal from the study and SAEs.

Laboratory values, vital signs, and weight will be summarized by period and visit. Possibly clinically significant treatment-emergent abnormalities for laboratory values, vital signs, and weight will be listed and summarized by period and visit. Electrocardiogram abnormalities, as well as physical and neurological abnormalities, will also be listed by period and visit.

Hospital anxiety and depression scales will be analyzed for the POS/PGS subpopulation only.

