13.3 Statistical and Analytical Issues

13.3.1 Handling of Dropouts or Missing Data

Safety and efficacy variables will be analyzed as they are available. Days with missing information will be ignored in the calculation of the seizure frequency and seizure days.

confidential information and ucb property

This document cannot be used to support any marketing authorization application and any extensions or variations thereof.

Since subjects will drop out at different times from the study, results will be presented by categories of duration of exposure.

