3.2.7 Exposure duration and exposure duration cohorts

At the final analysis, the overall duration of exposure (or On Treatment Period) will be calculated as the date of last dose of BRV minus the date of first dose of BRV plus 1 day. Each subject will be classified into one or more of the following exposure duration cohorts based on the duration of BRV exposure as calculated above:

All subjects	≥1 day
≥3 months	≥90 days
≥6 months	≥180 days
≥12 months	≥360 days

This categorization will continue in 6-month increments past 12 months up to a time point that will be determined based on cumulative exposure at the time of the database lock.

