4.2 Handling of dropouts or missing data

Seizure frequency (subjects with POS) and seizure days (subjects with PGS) will be calculated over non-missing diary days during each study period or time interval as described in Section 3.2.4 and Section 3.2.5; diary days for which seizure data were not obtained will not be considered in the calculation of seizure frequency or seizure days. Because the evaluation of efficacy is not the primary objective of this study, and because this is an uncontrolled study in a variable setting, which allows individualized optimization of dosing of BRV and concomitant AEDs, no summaries assessing the impact of missing seizure diary days are planned.

For subjects who prematurely discontinue during the Evaluation Period, the calculation of POS frequency and PGS seizure days will be based on available seizure diary while the subject was receiving BRV. The presence of such dropouts may influence the evaluation of the long-term outcomes for subjects who either do not discontinue or do not discontinue early in the study. Therefore, as described below, selected summaries will be produced by exposure

duration cohorts to allow an assessment of long-term outcomes without the potentially confounding influence of earlier discontinuations.

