8.1.1 Partial onset seizure frequency

Twenty-eight day adjusted POS frequency will be summarized with quantitative descriptive statistics for all subjects for the Baseline Period, the On Treatment Period, and by 3-month time intervals over the On Treatment Period. The summary over the On Treatment Period will include all subjects in the POS Efficacy Analysis Set. Similar summaries will be provided for the full cohort interval and by 3-month time intervals for each exposure duration cohort.

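### SAEs and AE withdrawals, two of the three primary safety variables, get no table by duration of exposure or time in the SAP, although the protocol promises one for each

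*SAP*

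**What the plan says.** Protocol 13.1.3 says of safety in general: "Summary tables will be presented over the Evaluation Period by time windows, by periods, and by categories of total duration of exposure". It then commits specifically on these two outcomes: "Separate tables will be provided, by categories of total duration of exposure, for AEs leading to withdrawal from the study and SAEs". Protocol 13.3.1 gives the reason: "Since subjects will drop out at different times from the study, results will be presented by categories of duration of exposure".

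SAP 2.2.1.1 keeps SAEs and withdrawal due to AE as primary safety variables, beside TEAEs. SAP 11.2.2 then lists the SOC/PT tables. These two outcomes get one line each: "Incidence of treatment-emergent SAEs" and "Incidence of TEAEs leading to permanent discontinuation of study drug". Neither line carries a qualifier, so by that section's default each pools the Evaluation, Down-Titration and Post-Treatment Periods. The overall AE summary also counts subjects with these events, but breaks them down only by region and indication.

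For the first secondary efficacy variable, SAP 8.1.1 says: "Similar summaries will be provided for the full cohort interval and by 3-month time intervals for each exposure duration cohort". SAP 8.1.2 and 8.1.3 do the same for percent reduction and responders.

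**The concern.** The study follows subjects for years and they leave at different times. A single crude percentage over the whole study mixes subjects treated for weeks with subjects treated for five years. It cannot show whether SAEs or AE withdrawals cluster after entry, continue at a steady rate, or become more frequent with longer treatment. That is what a study of long-term safety is expected to describe.

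The SAP recognises the problem for seizure outcomes. Section 4.2 uses "duration cohorts to allow an assessment of long-term outcomes without the potentially confounding influence of earlier discontinuations". The plan would therefore describe the course of efficacy, a secondary objective, but not of two of the three primary safety variables.

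**Working it through.** The plan states no figure to reproduce: the study is descriptive, with no sample size calculation. The check compares the two documents and then illustrates what is lost.

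**Count of SOC/PT tables in SAP 11.2.2**

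| Group | Tables | Split by time or period | Split by exposure duration |
|---|---|---|---|
| Overall incidence | 6 | 3 (all TEAEs by 3 months; all TEAEs by study period; TEAEs in at least 5% by 3 months) | 0 |
| Intensity and causality | 2 | 0 | 0 |
| SAEs | 1 | 0 | 0 |
| Discontinuation | 1 | 0 | 0 |
| TEAEs of interest | 2 | 1 (by 3 months) | 0 |
| Total | 12 | 4 | 0 |

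None of the four split tables isolates SAEs or AE withdrawals. On the efficacy side, three of three secondary variables have both 3-month intervals and exposure cohorts.

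**Could another part of the SAP supply the tables?**

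- Section 3.2.5 says 3-month intervals apply to AEs. That is a general inclusion rule; 11.2.2 names the tables that use it, and these two are not among them.
- The all-TEAE interval tables contain these events but do not identify them.
- The Kaplan-Meier estimates in 5.1 treat permanent discontinuation for any cause as the event.
- The exposure cohorts in 3.2.7 are not called by any AE table.
- Listings (3.1) hold the subject-level data but are not summary tables.

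**Illustration**

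Inputs from the SAP: 859 enrolled, 6 of them from N01315 (2.4). The Safety Analysis Set excludes those 6 (3.5.1), so N is at most 859 − 6 = 853. The last Kaplan-Meier time point is 60 months (5.1), which gives 20 intervals of 3 months. Assumptions not in the documents: a crude AE-withdrawal total of 5%, that is 0.05 × 853 = 42.65, about 43 subjects; and constant dropout for other reasons that alone would leave R = 30%, 50% or 70% at 60 months.

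With monthly hazards, λ = −ln(R)/60 for other dropout and h for AE withdrawal while that risk is active. Incidence in an active interval, among subjects on drug at its start, is

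p = h/(λ+h) × [1 − exp(−3(λ+h))],

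with h solved so that events over all 20 intervals total 5% of N.

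For R = 50%, λ = 0.01155:

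- Months 1–6 only: h = 0.00885, p = 0.434 × 0.0594 = 2.58%. Events are about 22.0 + 20.7 = 42.7.
- Constant: h = 0.00119, p = 0.0934 × 0.0375 = 0.35%. The total is 0.0934 × [1 − exp(−0.764)] = 5.0%.
- After Month 36 only: h = 0.00377, p = 0.246 × 0.0449 = 1.11%. The total is 0.660 × 0.246 × [1 − exp(−0.368)] = 5.0%, where 0.660 is the share still on drug at Month 36.

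| Course of risk | R = 30% | R = 50% | R = 70% |
|---|---|---|---|
| Months 1–6 only, per interval | 2.61% | 2.58% | 2.55% |
| Constant, per interval | 0.43% | 0.35% | 0.30% |
| After Month 36 only, per interval | 1.66% | 1.11% | 0.85% |

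The overall row of the planned discontinuation table reads 5.0% in every cell of this grid.

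**The case against.** The strongest reply is that two different things are being asked for. Categories of total exposure, which the protocol promises for these outcomes, group subjects by how long they stayed; they do not show when an event began. Timing comes from an interval table, whose only protocol basis is the general reference to time windows in 13.1.3. This is right, and it means that meeting the specific promise alone would not show the course of risk. It does not remove the mismatch, because the SAP gives these outcomes neither split.

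Second, the comparison with efficacy is imperfect. Seizure frequency can be summarised within nested cohorts, whereas an AE withdrawal ends exposure. That stands, and it affects the form of the remedy. The contrast shows only that efficacy gets a time course and these outcomes do not.

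Third, columns would be sparse. With about 43 events over 20 intervals, the constant-risk case gives roughly two subjects per 3-month column before any SOC/PT breakdown. That also stands, and applies to nearly every column rather than only the late ones.

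Fourth, the listings would let a reader work out onset times. They would, but that leaves the reader to build the promised tables.

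Fifth, silence in the SAP's amendment section proves nothing, since the preceding SAP may also have lacked these tables. Agreed; the finding does not rely on it.

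**Conclusion.** The concern holds. The protocol's commitment is explicit, and the SAP neither delivers it nor says why: 0 of 12 listed AE tables are by exposure duration, and 0 of the 4 time- or period-split tables isolate SAEs or AE withdrawals. These counts rest on the text alone. The percentages in the illustration rest on an assumed 5% and assumed retention. The qualitative conclusion, that one overall percentage carries no information on timing, does not depend on them. The protocol speaks of withdrawal from the study and the SAP of stopping study drug; the split is missing under either wording. The departure is also somewhat wider, because 13.1.3 promises TEAEs in general by exposure category and the SAP uses 3-month intervals and study period instead. The point should be corrected before reporting. It affects the description of the primary objective but no test, and no data are lost.

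**What to change.** In SAP 11.2.2 add, for treatment-emergent SAEs and separately for TEAEs leading to permanent discontinuation:

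1. Incidence by the 3-month intervals already used for all TEAEs, with subjects on BRV in the interval as denominator and onset up to the last dose, as 11.2.2 already defines. Collapse to 6 or 12 months where counts are small.
2. Incidence by mutually exclusive categories of total exposure built from the 3.2.7 cut-points: under 3, 3 to under 6, and 6 to under 12 months, then 6-month steps.

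Do not use the 3.2.7 cohorts themselves for table 2. They are nested ("Each subject will be classified into one or more of the following exposure duration cohorts"), so a subject who withdraws in month 2 appears only under all subjects. State that percentages in table 2 are conditional on when subjects left, so timing is to be read from table 1. Exposure-adjusted first-event rates are optional; if added, count only events with onset up to the last dose, so that numerator and time at risk match.

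If the tables are left out on purpose, give the reason in the SAP and let it also cover the missing exposure split for TEAEs in general.

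The cost is four descriptive tables (two outcomes, two splits) from onset dates, intervals and exposure durations the SAP already defines. The downside is sparse columns, which collapsing reduces.
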